### 2.8.3.3 Vital signs

All vital signs data will be listed by participant and time point (including pre and post injection data points as applicable), and if reference ranges are available, abnormalities will be flagged.

For vital signs data collected at Month 6 and Month 12, summary statistics for change from baseline will be provided.

**Pre-injection** vital sign assessments will be defined as the assessment result obtained 30-60 (+/- 10 min) minutes pre-injection of the study drug, and **post-injection** vital sign assessments will be defined as the assessment result obtained 60 minutes post-injection of the study drug.

Height will be collected at screening visit only and will be summarized in the baseline characteristics summary only.

Notable vital sign abnormalities will be summarized. Notable vital sign abnormalities are defined in [Table 2-10](#).

**Table 2-10 Criteria for notable vital sign abnormalities**

Vital sign	Criteria for notable abnormality
Pulse (bpm)	<50 or >120 bpm
Systolic blood pressure (BP) (mmHg)	<90 or >180 mmHg
Diastolic BP (mmHg)	<50 or >205 mmHg
Temperature (°C)	<35 or >40 °C
Body weight (kg)	<30 or >180 kg

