8.4.3 Vital Signs

Vital signs will include sitting pulse rate (measured as radial pulse for 60 seconds), sitting systolic and diastolic blood pressure and body temperature (oral, or per local practice and should be recorded in the relevant CRF page in Celsius) which will be assessed at the visits indicated in [Table 8-1](#) and [Table 8-2](#).

After the participant has been sitting for five minutes, with back supported and both feet placed on the floor, systolic and diastolic blood pressure will be measured three times using an automated validated device, e.g. OMRON, with an appropriately sized cuff. At the baseline visit only, systolic and diastolic blood pressure should be measured 3 times. The repeat sitting measurements will be made at 1 - 2 minute intervals and the mean of the three measurements will be used. In case the cuff sizes available are not large enough for the participant's arm circumference, a sphygmomanometer with an appropriately sized cuff may be used.

Vital signs should be obtained 30-60 (+/- 10min) minutes before the subcutaneous injection (study drug). If premedication is required, the vital signs should be taken prior to premedication administration.

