10.1 Definition of adverse events and reporting requirements

10.1.1 Adverse events

An adverse event (AE) is any untoward medical occurrence (e.g. any unfavorable and unintended sign [including abnormal laboratory findings], symptom or disease) in a participant or clinical investigation participant after providing written informed consent for participation in the study. Therefore, an AE may or may not be temporally or causally associated with the use of a medicinal (investigational) product.

In addition, all reports of intentional misuse and abuse of the product are also considered an adverse event irrespective of if a clinical event has occurred.

Novartis qualified medical personnel will be readily available to advise on trial related medical questions or problems.

The occurrence of adverse events must be sought by non-directive questioning of the participant at each visit during the study. Adverse events also may be detected when they are volunteered

by the participant during or between visits or through physical examination findings, laboratory test findings, or other assessments.

Abnormal laboratory values or test results constitute adverse event only if they fulfill at least one of the following criteria:

- they induce clinical signs or symptoms
- they are considered clinically significant
- they require therapy

Clinically significant abnormal laboratory values or test results must be identified through a review of values outside of normal ranges/clinically notable ranges, significant changes from baseline or the previous visit, or values, which are considered non-typical in participants with the underlying disease. Investigators have the responsibility for managing the safety of individual participant and identifying adverse events. Clinically notable laboratory findings are defined according to the Common Terminology Criteria for Adverse Events (CTCAE) (the most current version will be used and can be found on the following web-site: <http://ctep.cancer.gov>).

Adverse events must be recorded under the signs, symptoms, or diagnosis associated with them, accompanied by the following information (as far as possible) (if the event is serious refer to [Section 10.1.2](#)):

- The Common Toxicity Criteria (CTC) AE grade (1-4)

If CTCAE grading does not exist for an adverse event, use:

1 = mild: usually transient in nature and generally not interfering with normal activities

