12.5.2 Safety endpoints

For all safety analyses, the safety set will be used. All listings and tables will be presented by treatment. Unless explicitly otherwise stated, only data up to and until B cells are repleted after the final study drug administration for study completers or until the participant initiates a commercial MS disease modifying therapy or until the end of Safety Follow-up for premature withdrawals will be included in the analysis and data beyond this time point for a participant will be excluded from safety analysis. In addition, a separate summary for death including on treatment and post treatment deaths will be provided. In particular, summary tables for adverse events (AEs) will summarize only on-treatment events, which started or worsened during the on-treatment period (treatment-emergent AEs).

The on-treatment period for safety analysis lasts from the date of first administration of study drug until B cells are repleted after the date of the last actual administration of study drug for study completers or until the participant initiates a commercial MS disease modifying therapy or until the end of Safety Follow-up.

Adverse events

All information obtained on adverse events will be displayed by treatment and participant. The number and percentage of participants with AEs of special interest/related to identified and potential risks will be summarized in the following ways:

[figure not shown]
- By treatment, primary system organ class and preferred term.
- By treatment, primary system organ class, preferred term and maximum severity.
- By treatment, pre-defined topic of interest, primary system organ class and preferred term.

Separate summaries will be provided for study medication related adverse events, serious adverse events, and other significant adverse events leading to discontinuation.

The number and percentage of participants with adverse events of special interest will be summarized by treatment, primary system organ class and preferred term. A participant with multiple AEs within a category is only counted once towards the total of that category.

Vital signs

All vital signs data may be listed by participant, and visit. Abnormalities will be flagged. Descriptive statistics for change from baseline will be provided by visit.

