#### **Multiple assessments**

It is possible that multiple assessments of a patient fall into the same visit-window (e.g., due to unscheduled visits). All results (scheduled and unscheduled) will be displayed in listings, but only one value (observed or derived) will be selected for summary statistics by visit-window.

For quantitative variables, the assessment closest to the target day will be selected. If more than one assessment is at the same distance to the target day, the later one will be selected.

For tables displaying the worst case scenario, such as shift tables or notable abnormalities, all assessments within a visit window will be used to identify the worst (e.g. the maximum or the minimum depending on parameter).

- **Baseline:** The last non-missing measurement made prior to or on the date of administration of the first dose of study treatment (the reference start date / Day 1). Only date part is considered if just one assessment on Day 1. If there are multiple assessments on Day 1, the following rules will apply:
  - a. If assessment time exists,
    - select the last available measurement prior to reference start date/time considering time;
  - b. If assessment time does not exist, select the available measurement from the lowest CRF visit number.
- **Post-baseline:** The measurement closest to the target day will be used. In the event two measurements are taken equally apart (e.g., 1 day before target date and 1 day after), the later one will be used. Cases where the same parameter is recorded more than once on the same date will be handled as follows:
  - a. If time of completion exists, the latest measurement will be used;
  - b. If time does not exist, the measurement from the lowest CRF visit number will be used.

In case categorical variables are based on continuous variables, the visit will be assigned to the continuous variable, and this visit will be used for the derived categorical variable.

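### SAP Table 2-10: the upper limit for notable diastolic pressure (>205 mmHg) lies 25 mmHg above the systolic limit (>180 mmHg), so it can flag no one the systolic row has not already flagged

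*SAP*

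**What the plan says.** SAP section 2.8.3.3 plans a summary of notable vital signs: "Notable vital sign abnormalities will be summarized. Notable vital sign abnormalities are defined in" Table 2-10. That table gives systolic pressure as "<90 or >180 mmHg" and diastolic pressure as "<50 or >205 mmHg".

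Three other passages bear on how the limits operate:

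- **Measurement.** Protocol 8.4.3 takes the two pressures together in one sitting measurement: "systolic and diastolic blood pressure will be measured three times using an automated validated device". The mean of the three measurements is used. The same section then restricts the triple measurement to the baseline visit, and SAP 2.1.1.5 defines averaging for baseline only.
- **Choice of value.** For worst-case tables, the SAP's rules on multiple assessments (under 2.4.2) state: "such as shift tables or notable abnormalities, all assessments within a visit window will be used to identify the worst".
- **Other limits.** Protocol 12.5.2 says vital sign abnormalities will be flagged but gives no numbers. Neither document states another diastolic limit or explains the 205.

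**The concern.** An upper diastolic limit set above the upper systolic limit cannot do the work of a separate criterion. To exceed it, a participant must already be well past the systolic limit. The diastolic row then repeats part of the systolic count and misses the case it exists to catch, which is high diastolic pressure while systolic is within limits.

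The study has a single arm and no data monitoring committee (Protocol 4.3 and 10.2.4), so descriptive safety tables carry much of the safety evidence. A zero in the high-diastolic line would follow from the limit, not from the participants' blood pressure, and the table gives the reader no way to tell the difference.

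**Working it through.** **Inputs.** From SAP Table 2-10: upper systolic limit 180, upper diastolic limit 205, lower systolic limit 90, lower diastolic limit 50 (all mmHg). Assumption: diastolic (D) does not exceed systolic (S) in a valid reading.

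**Gap between the limits.** 205 - 180 = 25 mmHg, with the diastolic limit the higher.

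**Does D > 205 ever flag someone whom S > 180 does not?**

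1. *Single reading.* If D > 205, then S ≥ D > 205 > 180. The systolic row has already flagged the reading.
2. *Mean of three readings.* D ≤ S in each reading gives mean D ≤ mean S. If mean D > 205, then mean S > 205 > 180. The result is therefore the same whether averaging applies at every visit or at baseline only.
3. *Worst value in a visit window.* The highest D and the highest S may come from different readings. The reading with the highest D has S at least as high, so max S ≥ max D. If max D > 205, then max S > 205 > 180.

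Under all three rules, the participants flagged by the upper diastolic limit are a subset of those flagged by the upper systolic limit.

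**Enumeration as a check.** Take all whole-number pairs with S from 40 to 300 and D from 20 up to S. These ranges are chosen only to cover the limits; the counts test the logic and do not estimate how many participants are affected.

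- Total pairs: for each S there are S - 19 values of D. The sum of 21 to 281 is 261 × 151 = 39,411.
- Pairs with D > 205: S runs from 206 to 300, giving 1 + 2 + ... + 95 = 95 × 96 / 2 = 4,560. The smallest S among them is 206.
- Pairs with D > 205 and S ≤ 180: 0.

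**What limit could add anyone?** For an upper diastolic limit L below 180, the pairs with D > L and S ≤ 180 number (180 - L)(181 - L) / 2. At L = 179 this is 1 × 2 / 2 = 1, the pair 180/180. At L = 180 or above, including 205, it is 0.

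**What goes uncounted.** With S between 90 and 180, every D from 50 up to S passes the whole table unflagged. The highest unflagged diastolic value is 180 mmHg.

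**Lower limit.** D < 50 with S between 90 and 180 gives 30 × 91 = 2,730 pairs flagged by the diastolic row alone. That half of the row works.

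**The case against.** The strongest reply is that little depends on this cell. It is half a row in a descriptive table of a study without hypothesis testing. Vital signs are not among the key safety assessments in the protocol summary and are not in the interim analysis. Exclusion criterion 16 keeps out uncontrolled arterial hypertension, so few affected participants are expected. All of this stands, and it limits the weight of the point without making the limit work.

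It can also be said that high diastolic values would surface elsewhere:

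- SAP 2.8.3.3 lists all vital signs, with abnormalities flagged if reference ranges are available.
- The same section adds: "For vital signs data collected at Month 6 and Month 12, summary statistics for change from baseline will be provided". The protocol likewise says: "Descriptive statistics for change from baseline will be provided by visit". The SAP's standard summary statistics include the maximum.
- Raised pressure may be tabulated by participant as an adverse event.

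These outputs do exist, but none replaces the missing count. Under the SAP's multiple-assessment rules, by-visit statistics use the value closest to the target day, not the worst in the window. A maximum describes one value and does not say how many participants were high. Adverse event tables do count participants, but on a different basis, because Protocol 10.1.1 makes reporting conditional: "Abnormal laboratory values or test results constitute adverse event only if they fulfill at least one of the following criteria". Those criteria are symptoms, clinical significance or need for therapy, so the count does not follow a fixed threshold.

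Two technical reservations remain. A record with a missing or invalid systolic value could be flagged by the diastolic row alone; that is a data query and lies outside the stated assumption. A misprint or misreading of the digits also cannot be ruled out from the text alone, and checking the value against its source would settle that.

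**Conclusion.** The concern holds. As printed, the upper diastolic limit in SAP Table 2-10 has no effect of its own: it exceeds the systolic limit by 25 mmHg and adds no participant to those the systolic row flags. The conclusion rests only on diastolic not exceeding systolic in a valid reading, and it holds for single readings, means and worst-in-window values.

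The consequence is one planned safety criterion that cannot operate, with a high-diastolic count that is near-certain to be zero for that reason. The number of participants affected cannot be derived from the documents. The defect does not touch the lower diastolic limit, the systolic row, or any primary or secondary endpoint. It should be corrected, but it does not threaten the study's main conclusions.

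**What to change.** Check the 205 mmHg value against the source of Table 2-10 and reconcile it with the systolic limit in the same table. To identify anyone beyond the systolic row, the upper diastolic limit must lie below 180 mmHg. That is only an arithmetic bound: the documents do not give the intended value, and the sponsor must supply it.

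Correct the number in the SAP and in the program before the notable-abnormality table is produced, or rerun that table if it already exists. The cost is one number in each place and at most one rerun, with no new data.

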### 2.9 Pharmacokinetic endpoints

There are no pharmacokinetic endpoints planned for this study.

### 2.10 PD and PK/PD analyses

There are no PD and PK/PD analyses planned for this study.

### 2.11 Patient-reported outcomes

#### 2.11.1 Treatment Satisfaction Questionnaire for Medication-9 (TSQM-9)

The Treatment Satisfaction Questionnaire for Medication-9 (TSQM-9) is a 9-item general instrument that measures the major dimensions of satisfaction with a medication ([Bharmal et al. 2009](#)). Scores will be calculated for the effectiveness (Items 1-3), convenience (Items 4-6) and global satisfaction scale (Items 7-9). See [Appendix Section 5.4.2](#) for the scoring algorithm. Scores on the TSQM scale range from 0 (indicating poor satisfaction) to 100 (indicating perfect satisfaction).

Change from baseline in TSQM-9 scores for all 3 domains (effectiveness, convenience and global satisfaction) to Month 6 and 12 will be summarized for the FAS.

[REDACTED]

[REDACTED]

[REDACTED]

## 2.12 Biomarkers

[figure not shown]
### 2.12.1 B and T cell counts

[figure not shown]
Change from baseline in lymphocytes, including total CD19+ B cell counts and CD20+CD3+ T cell counts, obtained by FACS will be summarized descriptively by time point for the SAF. Both absolute and percentage counts will be presented.

In addition, number and percentage of participants with B cells < the lower limit of normal (LLN) or < their baseline value (i.e., B cell depleted) will be presented by time point.

[REDACTED]

[REDACTED]

## **2.14 Interim analysis**

For the purpose of earlier dissemination of results, an interim analysis will be performed after all enrolled participants have either met the criteria of at least 6 months treatment or discontinued treatment prematurely. For this analysis, only primary variables, demographics, baseline characteristics, adverse events and serious adverse events will be summarized. The cut-off for the interim analysis will be the Month 6 visit date. Data up to the cut-off date will be presented.

Since there will be no hypothesis testing involved, statistical adjustment for the interim analysis will not be made at the stage of final analyses of efficacy and safety.

## **3 Sample size calculation**

Sample size calculations were based on the proportion of participants with no change or a reduction from baseline in the number of GdE MRI lesions 12 months after initiating ofatumumab therapy. Three precision estimates were considered for this study:

The sample size of 100 participants is selected based on budget and early availability of interim analysis results. This sample size of 100 participants will provide us with an 8.5% precision (half-width of 95% confidence interval), a 7.8% precision, or a 7.0% precision corresponding to estimated proportions of 75%, 80%, and 85% of participants achieving the primary endpoint.

## 4 Change to protocol specified analyses

Please see [Table 4-1](#) Change to protocol specified analyses below for a list of changes to protocol specified analyses are tabulated below.

**Table 4-1 Change to protocol specified analyses**

Section(s) of the protocol	Change
No changes	Not Applicable

## 5 Appendix

### 5.1 Imputation rules

#### 5.1.1 Study drug

There will be no imputation rules for study drug detailed for this study.

#### 5.1.2 AE date imputation

The following table explains the notation used in the logic matrix. Please note that missing start dates will not be imputed.

	Day	Month	Year
Partial Adverse Event Start Date	Not used	MON	YYYY
Treatment Start Date (TRTSTD)	Not used	TRTM	TRTY

The following matrix explains the logic behind the imputation.

	MON MISSIN	MON<TRTM	MON=TRTM	MON>TRTM
YYYY MISSIN	NC Uncertain	NC	NC	NC
YYYY < TRTY	(D) Before Treatment Start	(C)	(C)	(C)
YYYY = TRTY	(B) Uncertain	(C) Before Treatment	(A) Uncertain	(A) After Treatment
YYYY > TRTY	(E) After Treatment Start	(A) After Treatment	(A) After Treatment	(A) After Treatment

The following table is the legend to the logic matrix.

If AE end date is complete and AE end date < Treatment start date or AE end date is partial and AE imputed end date < Treatment start date, then AE start reference = min (informed consent date, earliest visit date from SV) Else if AE end date is partial, AE end date  $\geq$  Treatment start date or AE is ongoing, then AE start reference = treatment start date.

Relationship	
Before AE start reference	Partial date indicates AE start date prior to AE start
After AE start reference	Partial date indicates AE start date after AE start
Uncertain	Partial date insufficient to determine relationship of AE start date to AE start
Imputation Calculation	
NC/Blank	No convention
(A)	MAX(01MONYYYY, AE start reference+1 day)
(B)	AE start reference+1
(C)	15MONYYYY
(D)	01JULYYYY
(E)	01JANYYYY
Complete date	No date imputation

### Adverse Event End Date Imputation

Imputed date = date part of original date, if complete date

Imputed date = min (completion/discontinuation visit date, DEC 31, date of death), if month is missing

Imputed date = min (completion/discontinuation visit date, last day of the month, date of death), if day is missing

